#### 4.10 Exploratory Analyses

There will be no adjustments for multiplicity for any of the following exploratory analyses.

Results will be presented by treatment group.

##### 4.10.1 Treatment responders at Month 12 according to demographic and medical history subgroups

Response rates by treatment groups and treatment effect will be provided on the following subgroups:

- Region (North America, Europe, Australia)
- Gender (Male/Female)
- Race (White/Black or African American/Asian/Other)
- Subjects with / without history of asthma
- Subjects with / without history of allergy other than peanut
- Subjects with / without history of atopic dermatitis or eczema.

Analysis will be performed only on subgroups containing at least 15 subjects.

According to the sample size of each subgroup, exact 2-sided 95% CIs would be provided instead of a 2-sided Wald 95% CIs.

A forest plot will be provided summarizing the primary efficacy variable in the above subgroups.

##### 4.10.2 Analysis over time of IgE and IgG4 specific to peanut components

IgE and IgG4 specific to peanut components will include at least Ara h 1, Ara h 2, Ara h 3, Ara h 8 and Ara h 9.

The following variables will be tabulated, on the overall ITT population, by treatment group using descriptive statistics:

- IgE and IgG4 specific to peanut components at Baseline, M3, M6 and M12
- Change from Baseline in IgE and IgG4 specific to peanut components at M3, M6 and M12
- Relative change from Baseline in IgE and IgG4 specific to peanut components at M3, M6 and M12 calculated as:  
$$r = (\text{Value at Month M minus Value at Baseline}) / \text{Value at Baseline}$$

Repeated-measures ANCOVA models will be built to compare the mean absolute change from Baseline value IgE and IgG4 specific to peanut components using all time points evaluated up to M12 in the active Viaskin® Peanut 250 µg group versus the placebo group on the ITT population using observed data. The default variance/ covariance structure is “unstructured”.

The analysis performed will be the same as the one described in 4.8.4.1.

#### **4.10.3 Enumeration and characterization of reactions triggered by accidental consumption of peanut during the study and analysis of Risk taking behavior of subjects (voluntary consumption of peanut)**

The following results will be reported on the Safety population for each treatment group overall and by screening ED subgroup:

- Number and percentage of subjects with any (at least one) peanut consumption and number of consumptions (in classes: 1, 2,..)
- Number and percentage of subjects with any (at least one) confirmed accidental consumption of peanut and number of accidental consumptions (in classes: 1, 2,..)
- Number and percentage of subjects with any (at least one) not confirmed accidental consumption of peanut (assumed to be voluntary) and number of voluntary consumptions (in classes: 1, 2,..)
- Number and percentage of subjects with induced allergic reaction (overall and by type of symptom as classified by SOC and PT) (separately for confirmed and not confirmed accidental consumption)
- Number and percentage of subjects with treatment taken following accidental peanut consumption (overall and by type of treatment as classified by ATC class (level 3) and preferred drug name)

The above descriptions will be repeated on each age range (4 to 5 years, 6 to 8 years, and 9 to 11 years).

All data related to accidental/voluntary peanut consumption will be listed. These data include: confirmation (or not) of accidental consumption, food consumed, estimated quantity consumed at each occurrence, and associated reactions and severity of reactions. The cumulative reactive dose the subject reached at screening DBPCFC will also be presented in the listing.

All SAEs (allergic reactions) caused by consumption of peanut will be listed.

#### 4.10.4 Epigenetic modifications of the promoters of specific genes

Descriptive analyses of epigenetic modifications of specific genes in both treatment groups will be performed using actual values, change from baseline and relative change from baseline, for the overall ITT population, using observed data. Please Note that Epigenetic data will not be available at time of database lock.

#### 4.10.5 Safety sub-analysis in subjects with mutations in the filaggrin gene versus wild type subjects

The following safety sub-analyses (on the safety population) will be performed for the subjects with mutations in the filaggrin gene versus subjects carrying the wild type gene:

- Analysis of treatment-emergent adverse events: overview table of TEAE, frequency table of TEAEs, TEAEs considered related to IP and AESI by SOC and PT (as described in [Section 4.9.1](#)),
- Analysis of local skin reactions collected in the diary (as described in [Section 4.9.3](#)),
- Analysis of local skin reactions as graded by the investigator (as described in [Section 4.9.4](#)),
- Sensitization status to some other allergens (as described in [Section 4.10.6](#)),
- SCORAD evolution over time (as described in [Section 4.10.7](#)).

#### 4.10.6 Sensitization status to other allergens and their evolution over the study period

Observed data on allergen specific IgE to cow milk, egg white, pteronyssinus (house dust mites), and Timothy (grass pollen) will be reported using descriptive statistics on:

- Value at Baseline and M12,
- Change and relative change from Baseline at M12.

Shift tables presenting number and percentage of subjects with a value  $\geq$  or  $<$  0.7 kU/L at baseline and post-baseline assessments will be provided.

Additionally, shift tables will be presented using the categories (quartiles) as defined below:

- Minimum value to Q1
- Q1 (excluded) to median
- Median (excluded) to Q3
- Q3 (excluded) to maximum value.

A “missing” category will be added at M12 only. Results will be expressed on subjects with a non-missing value at Baseline.

This will be reported for the ITT population and repeated for subjects with filaggrin gene mutations versus wild type subjects.

#### 4.10.7 SCORAD evolution over time

SCORAD total score will be collected at Baseline, M3, M6 and M12.

SCORAD total score will be imputed as 0 if the subject answer “No” to the question:

”*Did subject have any areas of atopic dermatitis ?*” Summary statistics will be presented for:

- Value at Baseline, M3, M6 and M12 (actual values),
- Change from Baseline at M3, M6 and M12 (actual values).

This will be reported for the ITT population and repeated for subjects with filaggrin gene mutations versus wild type subjects.

#### 4.11 Patch adhesion

The Viaskin® patch adhesion will be evaluated during 28 days between M3 and M6 (whenever possible, these should be consecutive days - this assessment period can be extended up to M9 in case it has not been completed between M3 and M6).

The scoring system for adhesion and occlusion of Viaskin® patches (assessed at patch application and at patch removal) is indicated as follows:

- 0 = no lift off or detachment of the dressing edges and the occlusion chamber of the patch is intact.
- 1 = some edges of the dressing have lifted off the skin with no impact on the occlusion chamber of the patch which remains fully adherent to the skin.
- 2 = the occlusion chamber of the patch is partially or totally detached.
- 3 = the patch has fallen off the skin.

Even on those days when the patch has deliberately been removed prematurely by the subject or parents/guardians, the photos and assessment should be made as recommended, even if the assessment will not be used in the analysis. That is why the assessments may extend beyond 28 days to ensure that 28 days of usable evaluations of 24 hours of application are recorded.

Assessment of the adhesion of each patch will be made at 2 time points by the parents/guardians for 28 days:

- Immediately after the application of a patch to assess that the patch was applied as recommended and adhered well to the skin (including the edges of the dressing); and
- At the end of the 24-hours application period at time of removal of the patch.

At the time of each patch removal, the subjects (parents/guardians) will also be asked:

- To specify the status at removal of the patch (removal at 24±4 hours, deliberate removal before 24±4 hours, accidental removal),
- To specify the suspected cause of adhesion issue (if any: scratching, swimming, sweating...),
- To grade the ease of patch removal (very easy/ easy / difficult / very difficult),
- To grade whether the removal of the patch was painful (very painful / painful / slightly painful / not painful),

- To specify whether the patch removal caused skin injury (yes / no).

To guarantee the reliability of the adhesion scoring done by the subject's parents/guardians, the Investigator will review the parents/guardians' assessment of the patch adhesion based on the photographs made by the parents/guardians during these 28 days.

If the parents/guardians did not or could not assess the patch adhesion with sufficient reliability according to the Investigator's judgment and/or if the parents/guardians did not or could not take photos for a total of 28 days during M3 and M6, the Investigator can disqualify all or part of the data collected for the adhesion assessment and will re-train the parents/guardians so that the assessment of the patch adhesion can be repeated between M6 and M9 either totally for 28 evaluable days or partially to compensate for the disqualified days of the first period of assessment.

The assessment of adhesion of the Viaskin® patch will also be made at each site visit by site staff trained specifically for this purpose. The duration of application of the assessed Viaskin® patch must be noted, photographs must be taken and the assessment by the site staff will use the same scoring system as above.

A Per-Protocol Adhesion Set will include all evaluations except patches removed by the investigator (intentionally removed early, for example due to intolerable irritation) (i.e. : the investigator answered "No" to the question "do you confirm that the subject's evaluation is valid for the adhesion analysis?") . A listing of evaluations which will not be included in the PP Adhesion set will be provided.

The following tabulations will be provided:

- The number and percentage of patches evaluated overall and by adhesion grade, at time of application and at time of removal,
- The number and percentage of patches evaluated with an adhesion grade 2 or 3, at time of removal,
- The number and percentage of subjects with at least one patch evaluated with an adhesion grade 2 or 3, at time of removal,
- The number and percentage of patches by subject evaluated with an adhesion grade 2 or 3, at time of removal,
- The duration of application for patches with an adhesion grade 2 or 3 and for patches with an adhesion grade of 3,
- The suspected reason for adhesion issue (scratching / swimming / sweating / other/ unknown),
- The presence of skin injury due to removal (yes / no),
- The ease of removal (number and percentage of patches evaluated by category - very easy / easy / difficult / very difficult),
- The pain at removal (number and percentage of patches evaluated by category - very painful / painful / slightly painful / not painful).

Patch adhesion will be considered as acceptable if more than 90% of the patches at the expected time of patch removal, i.e. at 24±4 hours after patch application, have an adhesion score ≤1 as assessed by the subjects' parents/guardians. In other words, adhesion of the patch will be considered as acceptable if less than 10% of the patches are

evaluated with an adhesion grade 2 or 3 at time of removal, during the period of adhesion, for the overall population.

In addition, the population of subjects with more than 10% of their patches evaluated as a grade 2 or 3 will be studied and suspected reason(s) for adhesion issues for the concerned subjects will be tabulated. Response rate (primary efficacy variable) by treatment group and overall will also be presented descriptively on this population

The use of hypoallergenic adhesive dressing (e.g. Tegaderm®) to prevent possible patch adhesion issues was authorized on Dec 2, 2016 (at the time the last subject reached 4 months of treatment) and is collected in the eCRF (investigator assessment at study visits). Following a comment from the FDA, this decision was cancelled on Feb 2, 2017. As some subjects may have already used a hypoallergenic adhesive dressing, the number and percentage of subjects using at least one hypoallergenic adhesive dressing will be evaluated on the following periods:

- Between Month 3 (V7) and Month 6 (V8),
- Between Month 6 (V8) and Month 9 (V9),
- Between Month 9 (V9) and Month 12 (V10),
- Whole study period.

The quantity of dressing used (absolute and relative – compared to the total number of patches applied collected in the diary) with a hypoallergenic adhesive dressing used will also be tabulated.

For the adhesion assessment performed by the investigator at each visit, the following description will be tabulated:

- Number of subjects and percentage of subjects for each adhesion score at each time point.

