#### 1.1.1.2.3 VIPES Study: Phase IIb Efficacy and Safety Study (Completed)

This Phase IIb, double-blind, placebo-controlled study assessed the safety and efficacy of EPIT with Viaskin® Peanut in 221 peanut-allergic subjects (113 children, 73 adolescents and 35 adults) who were randomized to receive Viaskin® Peanut 50 µg, 100 µg, 250 µg, or placebo for 12 months.

With regard to efficacy, the primary efficacy endpoint was met. The treatment response rate in the whole population at Month 12 showed a statistically significant higher responder rate in the Viaskin® Peanut 250 µg group with 28 (50.0%) responders compared to 14 (25.0%) responders in the placebo group (p-value = 0.0108). The study population was composed of 2 age strata: children (6 to 11 years of age) and adolescents and adults (12 years and above). Fifteen (53.6%) children (6- to 11-years-old) were responders in the Viaskin® Peanut 250 µg group at Month 12 compared to 6 (19.4%) children in the placebo group (p-value = 0.0076). For the main secondary efficacy endpoints analyzed, there was a better response with the highest dose of Viaskin® Peanut (250 µg) than with the lower doses (50 µg and 100 µg) compared to placebo. The results for the children (6- to 11-years-old) were very favorable in all analyses, as differences

compared to placebo were generally even more pronounced with better statistical significance than the results seen in the whole population. In the adolescent and adult age strata, even though Viaskin® Peanut 250 µg showed higher effects for all endpoints analyzed, these were not statistically significant.

Generally, in terms of safety, Viaskin® Peanut patches at 50 µg, 100 µg or 250 µg peanut protein were well tolerated. The most common and most frequent AEs reported by the subjects were local cutaneous reactions at the sites of the patch application in more than 90% of the subjects treated with any dose of Viaskin® Peanut, versus 50% of the subjects in placebo. These local reactions were generally of mild or moderate severity, and resulted in withdrawal from treatment in only 2/221 (0.9%) of subjects.

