### 8.8 Patch adhesion

A frequency table showing the number of patches evaluated by the subjects' parents/guardians in their diaries and the proportion of patches for each adhesion score (see Section 6.2.9) will be presented, immediately after patch application and at time of patch removal.

Percentage of patches assessed by the subjects' parents/guardians and having an adhesion score equal to 2 (which means the occlusion chamber of the patch is partially or totally detached) or 3 (which means the patch has fallen off the skin) will be tabulated and the time to removal for those patches will be described.

Patch adhesion will be considered as acceptable if more than 90% of the patches at time of target patch removal, i.e. at 24±4 hours, have an adhesion score ≤1 as assessed by the subjects' parents/guardians.

Descriptive analysis will be conducted on the suspected causes of adhesion issues (scratching / swimming / sweating / other) and on the potential presence of skin injury(ies) caused by patch removal (yes / no), as assessed by the subjects (parents/guardians). Proportion of patches for each grade of patch removal easiness (very easy / easy / difficult / very difficult) and for each grade of pain at patch removal (very painful / painful / not painful), as assessed by the subjects (parents/guardians), will be tabulated.

Finally, the proportion of patches for each adhesion score as assessed by the Investigator at each time point will be tabulated.

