## 3 INVESTIGATIONAL PLAN

### 3.1 Overall Study Design and Plan

This is a 12-month, Phase III, double-blind, placebo-controlled, randomized study to assess the efficacy and safety of Viaskin® Peanut, dosed at 250 µg peanut protein (per patch) in peanut-allergic children from 4 through 11 years of age.

The overall maximum study duration for each subject is approximately 61 weeks (6-week screening period, 12-month treatment period and 2-week follow-up period).

During the maximum 6-week screening period, subjects will undergo a first screening visit and an entry double-blind, placebo-controlled food challenge (DBPCFC) to peanut to confirm their allergy and their entry peanut eliciting dose (ED). The starting dose of the challenge will be 1 mg peanut protein and will escalate up to a highest dose of 300 mg peanut protein. Subjects who react at or below the dose of 300 mg peanut protein are considered eligible. Randomization of eligible subjects will occur in a 2:1 ratio to Viaskin® Peanut dosed at 250 µg peanut protein (active treatment) or placebo. Subjects will be stratified at randomization by their entry/screening DBPCFC ED in one of the following two strata:

---

 PEPITES: A Double-blind, Placebo-controlled, Randomized Phase III Pivotal Trial to Assess the Efficacy and Safety of Peanut Epicutaneous Immunotherapy with Viaskin® Peanut in Peanut-allergic Children

- Stratum 1: children with a screening ED of 1 mg, 3 mg or 10 mg;
- Stratum 2: children with a screening ED of 30 mg, 100 mg or 300 mg.

The randomization scheme will ensure that the ratio of active treatment to placebo is maintained in each stratum.

Subjects randomized in the study and consenting for the genetic analysis on a voluntary basis will be assessed for mutations in the filaggrin gene. Subjects' participation for this genetic analysis will be optional.

Subjects will apply a Viaskin® patch containing either peanut protein or placebo daily for a period of 12 months. At Month 12, a second DBPCFC to peanut will be performed, with a starting dose of 1 mg peanut protein with escalation up to a highest dose of 2,000 mg peanut protein. This evaluation will help determine the primary efficacy endpoint of this pivotal study.

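### The patch-adhesion acceptance rule has no arm-level criterion; read naturally it pools active and placebo patches and may misjudge the active patch

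*SAP*

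**What the plan says.** SAP 4.11 states the rule twice. The positive form is "Patch adhesion will be considered as acceptable if more than 90% of the patches at the expected time of patch removal" score 0 or 1 on the parents' assessment. The negative form begins "In other words, adhesion of the patch will be considered as acceptable if less than 10% of the patches are" and continues "evaluated with an adhesion grade 2 or 3 at time of removal, during the period of adhesion, for the overall population". Protocol 8.8 has the same threshold, "Patch adhesion will be considered as acceptable if more than 90% of the patches at time of target patch removal", and mentions no arm.

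The adhesion outputs listed in SAP 4.11 carry no treatment split. The first is "The number and percentage of patches evaluated overall and by adhesion grade, at time of application and at time of removal"; the remaining parent-scored tables and the investigator-scored table are worded in the same way. The only by-arm output in the section concerns efficacy. For children with more than 10% of their patches graded 2 or 3, "Response rate (primary efficacy variable) by treatment group and overall will also be presented descriptively on this population".

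Allocation is unequal. SAP 3.1 says: "Randomization of eligible subjects will occur in a 2:1 ratio to" active or placebo.

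**The concern.** The rule yields a single verdict on adhesion, and the patch of practical interest is the one that carries peanut protein. If the arms are pooled, about one third of the denominator is a different product, and the verdict on the active patch depends partly on how well placebo patches stick.

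The documents give some reason to expect a difference. Protocol 1.1.1.2.3 reports, for the Phase IIb study, "local cutaneous reactions at the sites of the patch application in more than 90% of the subjects treated with any dose" of active patch, against 50% of placebo subjects. It adds that skin reactions were more severe on active at every time point. Protocol Table 5 shows that 13 of 26 observed children on 250 µg (8 + 5) had grade 2 or 3 reactions at Month 3, which is when the adhesion window opens; that table has no placebo column. Scratching is among the listed suspected causes of adhesion problems.

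What is at stake is whether the stated acceptance rule answers the question for the active patch. A pooled pass could cover an active patch that misses the 90% standard, and a pooled failure could condemn one that meets it.

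**Working it through.** **Inputs.** Randomized subjects: 220 active and 110 placebo (Protocol 8.10). Evaluable adhesion days: 28 per child (Protocol 6.2.9, SAP 4.11). Threshold: more than 90% with score 0 or 1, restated as less than 10% with grade 2 or 3 (SAP 4.11). Adhesion rates by arm are not given anywhere, so the placebo rates below are assumptions shown as a range.

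**The plan's own figure.** 100% − 90% = 10%, so the two forms of the threshold agree. No sample size, power or alpha is attached to the adhesion rule, so there is nothing further to reproduce.

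**Pooled rate.** Planned patches are 220 × 28 = 6,160 active and 110 × 28 = 3,080 placebo, 9,240 in all. Pooled failure = (6,160 × active + 3,080 × placebo)/9,240 = (2 × active + placebo)/3. To pass, failures must be below 10% of 9,240 = 924, so at most 923.

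| Placebo failure (assumed) | Placebo failures | Most active failures that still pass | Active failure rate |
|---|---|---|---|
| 0% | 0 | 923 | 14.98% |
| 2% | 62 | 861 | 13.98% |
| 5% | 154 | 769 | 12.48% |
| 8% | 246 | 677 | 10.99% |
| 10% | 308 | 615 | 9.98% |

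Solved for placebo, the limit is 30% − 2 × active. Active failure of 11%, 12%, 13% or 14% still passes if placebo failure is below 8%, 6%, 4% or 2%.

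**The opposite error.** The same formula shows an acceptable active patch failing. With active at 8%, the pooled rule fails once placebo reaches 30% − 16% = 14%. With active at 9%, it fails once placebo reaches 12%.

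**Criterion on active patches alone.** Passing needs fewer than 616 failures among 6,160, so at most 615 (9.98%), whatever happens on placebo.

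**Sensitivity.**
- With the 186 and 94 evaluable subjects of Protocol Table 10, there are 5,208 + 2,632 = 7,840 patches and at most 783 failures. The active limit is 15.03% with no placebo failures and 12.50% with placebo at 5%, nearly unchanged.
- SAP 4.11 removes evaluations of patches taken off early, for instance for irritation, from the Per-Protocol Adhesion Set. Suppose this left active children with 20 evaluable days against 28 on placebo (an assumption). Then there are 4,400 + 3,080 = 7,480 patches, and 10% is 748. The active limit becomes 748/4,400 = 17.0% with no placebo failures, or (748 − 154)/4,400 = 13.5% with placebo at 5%.

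**The case against.** **Pooling is not stated in so many words.** The SAP also uses the phrase overall population to mean not split by screening ED subgroup while keeping the arms apart, as in SAP 3.2 and 4.12. Table shells are in a separate document (SAP Appendix 4) and may have columns by arm. This stands as a caution: pooling is an inference, though the natural one. It does not remove the gap, because on either reading a yes/no rule lacks the arm to which it applies, and extra columns in a table would not supply that.

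**The evidence that the arms differ is indirect.** The Phase IIb percentages count any local reaction, at any dose, across children, adolescents and adults; they are not adhesion figures. The present patch has an added adhesive film that earlier studies lacked (Protocol 5.1). Excluding patches removed early takes out part of the proposed mechanism, and reactions mostly declined over time. All of this stands, so the masking is a possibility only.

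**Pooling is defensible for a device question.** Both arms wear the same patch system, differing in the peanut protein. That is a fair reason to report the pooled figure, but less so for making it the only test when irritation under the patch may affect adhesion.

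**A stronger reading.** A reader might infer that the rule decides whether the active arm received its dose as intended. The documents do not support that. SAP 4.7 plans exposure duration and compliance by treatment group, and separately summarizes daily hours of application and days without a patch. These do not capture partial detachment of a patch still worn, but the conclusion about dosing does not hang on one adhesion percentage. Nor does the rule touch the primary result: it lies outside the 14-step efficacy hierarchy.

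**Conclusion.** The point holds as a cheap improvement. The acceptance rule names no arm, no arm-level adhesion table is stated, and the natural reading pools the arms. Under 2:1 allocation with equal evaluable patches, active failure from 10% to just under 15% could be called acceptable if placebo adheres better, and an active patch within the standard could be rejected if placebo adheres worse. The upper limit moves only if evaluable days differ by arm. How likely either error is cannot be said from these documents.

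**What to change.** Before unblinding, add one sentence to SAP 4.11 stating that the acceptance criterion is evaluated in the Viaskin Peanut 250 µg group. Tabulate by treatment group all parent-scored and investigator-scored adhesion results, and also the evaluations excluded from the Per-Protocol Adhesion Set, so that unequal exclusion is visible. Keep the pooled figure as supportive.

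The data are already collected, so the cost is the sentence and additional table columns. The criterion would rest on about two thirds of the patches, roughly 6,160 of the 9,240 planned.

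### The 90% patch-adhesion rule in SAP 4.11 does not separate patches worn with the added dressing, so for late-enrolled or extended-assessment children the pooled rate may overstate adhesion of the patch alone

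*SAP*

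**What the plan says.** The acceptance rule in SAP 4.11 begins: "Patch adhesion will be considered as acceptable if more than 90% of the patches at the expected time of patch removal". It goes on to require a score of 0 or 1 as assessed by parents, and restates this as fewer than 10% of patches at grade 2 or 3 in the overall population. Protocol 8.8 has the same threshold: "Patch adhesion will be considered as acceptable if more than 90% of the patches at time of target patch removal".

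On timing, SAP 4.11 says that "patch adhesion will be evaluated during 28 days between M3 and M6" and that "this assessment period can be extended up to M9 in case it has not been completed between M3 and M6".

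On the dressing, use of a hypoallergenic adhesive dressing "to prevent possible patch adhesion issues was authorized on Dec 2, 2016", "at the time the last subject reached 4 months of treatment". Then: "Following a comment from the FDA, this decision was cancelled on Feb 2, 2017". Use is collected in the eCRF at study visits. The SAP tabulates users for Months 3-6, 6-9 and 9-12 and for the whole study, plus the quantity used, absolute and relative to patches applied.

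The only exclusion defined is this: "A Per-Protocol Adhesion Set will include all evaluations except patches removed by the investigator", explained as patches taken off early on purpose and identified by the investigator answering that the evaluation is not valid. Dressing use is not a criterion, and the SAP does not say that the 90% rule uses this set. SAP 4.13, which lists changes in conduct and analysis, does not mention the dressing.

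**The concern.** The rule is a statement about the study patch. Protocol 5.1 describes that patch as already carrying its own adhesive film, so the dressing authorized in December 2016 was something extra. Grades 2 and 3 mean a detached chamber or a fallen patch, which is the kind of problem the dressing was meant to prevent. A dressed patch that scores 0 or 1 therefore does not show that the patch would have held without help.

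At stake is the pass or fail conclusion on adhesion. A second output could also shift: SAP 4.11 studies subjects with more than 10% of their patches at grade 2 or 3 and reports their response rate, and dressing use could move a child out of that group.

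**Working it through.** **The plan's own figure.** The two wordings of the rule agree: 1 − 0.90 = 0.10. With 28 scored patches per child, 280 to 330 children give 280 × 28 = 7,840 to 330 × 28 = 9,240 patches, and the rule fails at 784 to 924 patches of grade 2 or 3.

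**Who can overlap.** The authorization ran from 2 December 2016 to 2 February 2017, which is 62 days or about 2 months. The last subject was at Month 4 on the first date, so had started about 2 August 2016. Let m be a child's months on treatment on 2 December 2016, so m ≥ 4. The overlap with a window ending at Month E is max(0, min(E, m + 2) − m).

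| m | Overlap, Months 3-6 (E = 6) | Overlap, Months 3-9 (E = 9) |
|---|---|---|
| 4 | 2 months | 2 months |
| 5 | 1 month | 2 months |
| 6 | 0 | 2 months |
| 7 | 0 | 2 months |
| 8 | 0 | 1 month |
| 9 or more | 0 | 0 |

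The default window is touched only for m from 4 to under 6 (starts after about 2 June 2016). For m from 6 to under 9 (starts after about 2 March 2016), overlap needs an assessment extended past Month 6. The documents give no accrual curve. If accrual were uniform over an assumed 8 to 12 months, 2/12 to 2/8 = 17-25% of children would have calendar overlap with Months 3-6, and 5/12 to 5/8 = 42-63% with Months 3-9. These are upper limits on children affected, because a child must also have been scoring patches, and wearing the dressing, at that time.

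**How much dressing use would matter.** Let f be the share of scored patches that were dressed, and a_u and a_d the adherence of undressed and dressed patches. Then:

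pooled rate = (1 − f) × a_u + f × a_d

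and the share at which the pooled rate reaches 90% is f = (0.90 − a_u) / (a_d − a_u). The values of a_u and a_d are assumptions; the documents give none.

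| a_u | f if a_d = 100% | f if a_d = 95% |
|---|---|---|
| 89% | 0.01/0.11 = 9.1% | 0.01/0.06 = 16.7% |
| 88% | 0.02/0.12 = 16.7% | 0.02/0.07 = 28.6% |
| 85% | 0.05/0.15 = 33.3% | 0.05/0.10 = 50.0% |

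Read the other way, with a_d at 100% and 95% in turn, the lowest undressed adherence that still brings the pooled figure to 90% is 89.8% or 89.9% at f = 2%, 88.9% or 89.4% at f = 10%, and 87.5% or 88.8% at f = 20%.

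**The case against.** The strongest reply is that overlap may be rare in practice. The adhesion diary is dispensed at Month 3 and the 28 days should be consecutive where possible. A family that started at once would finish at about Month 4, which for the last subject enrolled is when the dressing was authorized. Overlap then needs a late start, interrupted days, or days disqualified and repeated. This stands as a limit on reach. It does not remove the point, because neither document requires an immediate start and both allow extension to Month 9.

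The SAP is also open about the dressing. Its usage tables would show whether use was negligible, and an investigator may mark an evaluation invalid. Both help only in part: the counts are not linked to scored patches or to the rule, and no instruction asks for dressed patches to be marked invalid.

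Finally, adhesion is a descriptive product criterion. It is not in the SAP's testing hierarchy and carries no alpha.

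Three stronger readings are tempting. A reader might infer that the whole cohort could use the dressing throughout its assessment; the dates rule that out. A reader might infer that use was concentrated in children whose patches detach, making a favourable bias certain; the SAP gives a preventive purpose but no selection criterion and no usage data, so this is conjecture. A reader might infer that a passing result would be an artefact; that needs undressed adherence below 90% and a sizeable dressed share, and neither is known.

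**Conclusion.** The point holds in limited form. As written, the 90% conclusion pools the patch alone with the patch plus dressing for late-enrolled children and for those with extended assessments, and no planned analysis shows whether the conclusion depends on this. The dressed patches stay in by omission; the SAP does not state a decision to include them. The effect is negligible if use was rare. It can change the conclusion only if undressed adherence is at or below 90%, and the further below it is, the larger the dressed share needed. That the error favours a pass rests on the assumption that dressed patches adhere at least as well as undressed ones. The efficacy hierarchy is not affected.

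**What to change.** State in SAP 4.11 that the 90% rule will be applied three ways:

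- (a) to all evaluations;
- (b) excluding evaluations dated from 2 December 2016 on that fall in a visit interval with recorded dressing use;
- (c) as a conservative bound, keeping those evaluations and counting them as grade 2-3.

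Conclude that the patch alone has acceptable adhesion only if (b) exceeds 90% and (c) does not reverse it. Otherwise report that the conclusion depends on dressing use.

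Exclusion alone is not enough. Use is recorded by visit and no link to single patches is described, so (b) may also drop undressed patches from the same children. If those adhered poorly, (b) would be pushed upward. The bound in (c) covers that risk but is severe: with a flagged share g, the remaining patches must adhere at more than 0.90/(1 − g), which is 91.8% at g = 2% and 94.7% at g = 5%, and it cannot be met at g = 10% or more. A failure in (c) therefore shows dependence on the flagged evaluations, not poor adhesion.

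The cost is a short SAP addition, one flag from eCRF dressing data matched to the dates of the adhesion evaluations, two more rows in a table, and possibly a less favourable adhesion figure.
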